- DKEFS Verbal Fluency Category Switching total (raw score)
- DKEFS Verbal Fluency Category Switching accuracy total (raw score)
- WAIS-IV Digit Span total (sum of forward, backward, sequencing raw scores)
- WAIS-IV Digit Span Forward total (raw scores)
- WAIS-IV Digit Span Backward total (raw scores)

- WAIS-IV Digit Span Sequencing total (raw scores)
- Continuous Performance Task (raw scores)

Functional Ability

- Catherine Bergego Scale total (raw score)
- Barthel Index total (raw score)

Quality of Life

- SF-12 Physical Composite Score
- SF-12 Mental Composite Score

Quality of Sleep

- Pittsburgh Sleep Quality Index total (sum of component scores)
- Pittsburgh Sleep Quality Index Sleep Efficiency (raw score)

The **primary analysis time point** is V2, the post-training assessment. The **secondary analysis time point** is V3, the follow-up assessment.

The **primary statistical analysis methodology** is a linear mixed-effects model approach. We will first compare treatment and active control groups in the ITT population to determine if any differences in baseline demographic, characterization, outcomes variables, or total program use time remain after the randomization process. Any such factors that show trend level significant differences ($p < 0.1$) will be noted and used as covariates in the linear mixed model analysis. We will examine the data from each outcome measure using a linear mixed model with group and time as fixed factors, site as a random factor, and co-variates as necessary from the baseline analysis. Missing data will be handled with an iterative maximum likelihood procedure to optimally estimate model parameters. The key value for significance will be the group-by-time interaction factor for the model. This modeling will be conducted with a Type I error set at 0.05 for each model.

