Secondary, exploratory analysis will test for effects in exercise-based progress as well as by domain (e.g., working memory, attention, processing speed) to determine the unique benefit in each area of attention, cognition and independent function. First, to determine if the treatment effect varies based on participants' clinical severity of neglect (Mesulam total misses) or symptom subtype (e.g., sensory loss vs. intact sensory systems), we will correlate neglect severity (or subtype(s)) with gain scores on composite spatial cognition or executive performance and composite functional performance (as well as individual assessment measures). Additionally, we will measure whether improvements on certain components of the training program (e.g., improvements at inhibiting one's response to target stimuli) are associated with composite attention, executive or functional performance scores (as well as individual assessment measures). This could indicate whether certain patterns of training improvements are related more to improvements in attention, executive or functional performance. These analyses will be evaluated after correcting for multiple comparisons (i.e., Bonferroni).

The **criterion for statistical significance** is $p < 0.05$. Results greater than $p = 0.05$ and less than $p = 0.11$ will be described as trends.

To evaluate the effect of the experimental software treatment program (incorporating TAPAT) on spatial attention) we will conduct the analysis based on the pre-training (baseline) and post-training data.

Finding a significance level of $p < 0.05$ on the primary outcome measure will support the statement that the intervention improves spatial attention in the population.

To evaluate the endurance of effects following completion of the experimental software treatment program (incorporating TAPAT) we will use the same modeling approach based on the pre-training assessment (baseline) and end of study (follow-up visit) assessment data using a mixed-effects model parallel to those used to meet the primary and secondary aims. Finding a significance level of $p < 0.05$ on the primary measure will support the hypothesis that the training drives persistent improvement in spatial attention above and beyond an active control.

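### The follow-up (V3) rule lets a persistence conclusion be drawn on Field Bias without any effect having been shown at V2, the primary time point

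*SAP*

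**What the plan says.** All of this is in SAP section 1 (General Statistical Plan).

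- **Time points.** The primary analysis time point "is V2, the post-training assessment"; the secondary one "is V3, the follow-up assessment".
- **Test.** The plan names the test in these words: "The key value for significance will be the group-by-time interaction factor for the model".
- **Error rate.** The level is set separately for every analysis: "This modeling will be conducted with a Type I error set at 0.05 for each model".
- **V2 rule.** For the effect of the program, "we will conduct the analysis based on the pre-training (baseline) and post-training data". A p-value below 0.05 "on the primary outcome measure will support the statement that the intervention improves spatial attention in the population".
- **V3 rule.** For the endurance of effects, "we will use the same modeling approach based on the pre-training assessment (baseline) and end of study (follow-up visit) assessment data". If that p-value is below 0.05 for Field Bias, the result "will support the hypothesis that the training drives persistent improvement in spatial attention above and beyond an active control".

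No sentence orders the two tests, divides the 0.05 between them, or makes the V3 conclusion depend on V2. The only multiplicity correction named is Bonferroni. It is attached to the exploratory analyses of severity, subtype and training components.

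**The concern.** Persistence presupposes an effect at the end of training, and the SAP itself presents the V3 analysis as one of endurance. Yet the V3 model contains no V2 data, and its claim rule never looks at the V2 result. If V2 gave p = 0.60 and V3 gave p = 0.04, the plan as written would support a persistent improvement, although no effect at the end of training had been shown. The conclusion attached in advance to the V3 test says more than the test can show.

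There is a smaller, related point. The primary measure carries two pre-written favourable conclusions, each at its own 0.05 and with no order between them. The chance of reaching at least one of them when the program does nothing is therefore above that of a single test.

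**Working it through.** **Text.** The two rules side by side:

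| | V2 rule | V3 rule |
|---|---|---|
| Data in the model | baseline, V2 | baseline, V3 |
| Test | group-by-time | group-by-time (same approach) |
| Threshold | p < 0.05 | p < 0.05 |
| Conclusion | improvement | persistent improvement |
| Condition on the other visit | none | none |

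The last two rows do not fit together. The V3 conclusion refers to a course over time that includes V2, but nothing in the rule refers to V2. This follows from the text alone and needs no arithmetic.

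**Size.** The SAP gives no figure of its own to reproduce here. The inputs are:

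- 0.05 per model (SAP section 1).
- Two-sided tests, so a critical value of 1.96. This is assumed, because the SAP does not state sidedness.
- Correlation r between the V2 and V3 test statistics. This is not in the SAP and is assumed to be 0, 0.5 or 0.8.
- No true effect at either visit, with the two statistics Z2 and Z3 bivariate normal.

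Formulas:

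- At least one result favouring the program: 0.025 + 0.025 − P(Z2 > 1.96 and Z3 > 1.96).
- At least one significant result in either direction: 0.05 + 0.05 − P(|Z2| > 1.96 and |Z3| > 1.96).
- V3 favourable and V2 not favourable: 0.025 − P(Z2 > 1.96 and Z3 > 1.96).

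| | r = 0 | r = 0.5 | r = 0.8 |
|---|---|---|---|
| P(both favour the program) | 0.0006 | 0.0046 | 0.0110 |
| At least one favours the program (one test: 2.5%) | 4.9% | 4.5% | 3.9% |
| P(both significant, any direction) | 0.0025 | 0.0093 | 0.0219 |
| At least one significant, any direction (one test: 5%) | 9.75% | 9.1% | 7.8% |
| V3 favourable, V2 not favourable | 2.4% | 2.0% | 1.4% |

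Worked at r = 0.5: 0.050 − 0.0046 = 0.0454, or 4.5%, for at least one favourable result; 0.025 − 0.0046 = 0.0204, or 2.0%, for V3 alone. So about 0.0204 / 0.025 = 82% of chance-favourable V3 results would come without a favourable V2 result.

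**What a V2 condition would withhold.** Suppose the true effect is the same at both visits, with 80% power at each (assumed). V3 is then significant without V2 in 13% of trials at r = 0.3, 11% at r = 0.5, 9% at r = 0.7 and 5% at r = 0.9. In those trials a persistence conclusion would be true.

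**The case against.** The strongest case for the plan has four parts.

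1. **V3 is openly secondary.** The SAP names a single primary time point, V2. The V2 conclusion depends only on the V2 analysis, and V3 cannot rescue it. Many plans leave secondary analyses unadjusted. This stands. A reader might infer that V2 and V3 act as co-primary tests, so that the primary claim has an inflated error rate. The document does not support that: the V2 claim keeps its 5%. But the secondary label does not limit when the V3 conclusion may be drawn.

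2. **The V3 test is valid.** It compares change from baseline to follow-up between the groups, and a favourable result is evidence of a difference at follow-up whatever V2 showed. This also stands. It would be wrong to say that a V3 result without V2 shows nothing after training, because V3 is itself after training. What is missing is a demonstration at V2, and with it the basis for the word *persistent*.

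3. **Non-significance at V2 is not absence of effect.** This is correct, and it is the real cost of a V2 condition, as the 5% to 13% above shows. It does not justify the present rule, which allows the conclusion however weak the V2 result is.

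4. **The context suggests an order.** The endurance analysis is described after the V2 claim and reads as a follow-on. That narrows the gap, but it is not a stated condition.

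A reader might also take 7.8% to 9.75% as the rate of false benefit claims. Those figures include results that favour the control. The conclusions in the SAP are about improvement, so 3.9% to 4.9% against 2.5% is the relevant comparison.

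**Conclusion.** The point holds as a fault in the claim rule for V3, not in the model or in the primary analysis. As written, a significant baseline-to-V3 result on Field Bias supports persistence even when V2 showed no effect. That rests on the text alone.

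The effect on error rates is modest. Under the stated assumptions, the chance of at least one favourable result roughly doubles from 2.5% if the two statistics are uncorrelated, and rises less as the correlation grows. The figures are illustrative, since correlation, sidedness and power are not in the SAP. The change is worth making because a conclusion written in advance can be wrong and the correction is short.

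**What to change.** Add a fixed sequence for Field Bias to the endurance paragraph of SAP section 1:

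- Test V3 for the persistence claim at 0.05 only if the V2 group-by-time test is significant in favour of the program, and require the V3 result to favour the program too.
- Otherwise report the V3 between-group difference with its 95% CI as a follow-up difference, without the word *persistent*.

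With no effect at either visit, the chance of any false favourable claim across the two visits then returns to 2.5%. The chance of a false persistence claim falls from 2.5% to about 0.06%, 0.5% or 1.1% at r = 0, 0.5 or 0.8, which is the probability that both results favour the program.

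The cost is a sentence or two of text, and the V2 test loses no power. The downside is that an effect seen only at V3, or a real effect at both visits that misses significance at V2, is reported descriptively.

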To identify specific populations of treatment responders and non-responders) we will conduct exploratory data analyses post-hoc to examine predictors of treatment gain and predictors of lack of treatment gain based on baseline participant demographic, cognitive, and functional measures, as well as on learning rate and plateau performance measures derived over the course of the experimental software treatment program (incorporating TAPAT) use. We will initially employ single regression models to identify variables that predict change in cognitive and functional assessments, and then use generalized linear modeling to explore combinations of predictors of treatment gain or lack of gain.

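### The exploratory responder analysis relates change scores to baseline scores without the control arm, so a measure's own baseline can look like a predictor of response when there is no benefit

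*SAP*

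**What the plan says.** The last paragraph of SAP section 1 states its aim as "To identify specific populations of treatment responders and non-responders". It labels the work as "exploratory data analyses post-hoc to examine predictors of treatment gain and predictors of lack of treatment gain".

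- **Predictors.** Candidates are taken "based on baseline participant demographic, cognitive, and functional measures", together with learning-rate and plateau measures "derived over the course of the experimental software treatment program (incorporating TAPAT) use".
- **First step.** The plan uses "single regression models to identify variables that predict change in cognitive and functional assessments", that is, one predictor at a time with change as the outcome. It does not name the visit at which change is taken.
- **Second step.** The plan will then "use generalized linear modeling to explore combinations of predictors of treatment gain or lack of gain".

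The paragraph names no arm term, no arm-by-predictor interaction and no rule about the outcome's own baseline. It does not say whether one arm or both are used. Earlier in section 1, for the outcome models, the SAP says: "The key value for significance will be the group-by-time interaction factor for the model". Nothing extends that statement to the responder models. The Bonferroni correction in section 1 is attached to the preceding analyses of severity, subtype and training components.

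**The concern.** Cognitive and functional scores stand on both sides of these regressions, and nothing keeps a measure's own baseline out of the predictor list. Change is follow-up minus baseline, so error in the baseline score raises the predictor and lowers the outcome by the same amount. A participant who scored low by chance will on average score higher next time, with or without training. A single regression cannot tell that rebound from a benefit of training.

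What is at stake is the answer to the paragraph's own question. A variable could be reported as marking responders when it marks only measurement error, although the trial has an active control arm that shows the same rebound and would expose it.

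**Working it through.** The SAP gives no figure for this analysis, so there is none to reproduce.

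**Inputs from the SAP.** Section 1 lists nine cognitive measures (four verbal fluency scores, four Digit Span scores and the Continuous Performance Task) and two functional ones (Catherine Bergego Scale and Barthel Index), 11 in all. Digit Span total is the sum of its forward, backward and sequencing parts. The significance level is 0.05, taken here as two-sided.

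**Assumptions.** rho from 0.6 to 0.9, n of 30 or 50, equal variances at the two visits, and no benefit.

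**Direction.** Write baseline B = T + e1 and follow-up F = T + e2, with independent errors. Then cov(B, F - B) = cov(T + e1, e2 - e1) = -var(e1), which is negative whenever the baseline carries error. The same holds for the baseline of one Digit Span part against change in the total, because the part's error is inside the total. If a higher score is worse, the sign still means that the worst appear to improve most.

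**Size.** With equal variances, corr(B, F - B) = (rho - 1)/sqrt(2(1 - rho)) = -sqrt((1 - rho)/2). At rho = 0.7 this is -sqrt(0.15) = -0.39.

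**Chance of p<0.05.** By Fisher's z this is approximately Phi(atanh|r| x sqrt(n - 3) - 1.96). At rho = 0.7 and n = 50: 0.4086 x sqrt(47) = 2.80, and Phi(2.80 - 1.96) = Phi(0.84) = 80%.

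| rho | null correlation | n = 30 | n = 50 | apparent gain of worst third, (1 - rho) x 1.09 SD |
|---|---|---|---|---|
| 0.6 | -0.45 | 71% | 91% | 0.44 SD |
| 0.7 | -0.39 | 56% | 80% | 0.33 SD |
| 0.8 | -0.32 | 40% | 61% | 0.22 SD |
| 0.9 | -0.22 | 22% | 34% | 0.11 SD |

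A simulation of the same model (10,000 trials per cell), counting only significant results in the artefact's direction, gave 85%, 71%, 53% and 30% at n = 40 for rho 0.6, 0.7, 0.8 and 0.9. Over the wider grid of rho 0.6 to 0.95 and n of 20, 40 and 60, the range was 9% to 96%.

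**Scope.** With the baseline of a different test as predictor (true-score correlation 0.5, independent errors, n = 40), the rejection rate was 4.9% to 5.2%, about nominal. The 11 measures form 11 x 11 = 121 baseline-by-change pairings. Of these, 11 are own-baseline and 6 pair Digit Span total with a part. On independent errors the other 104 are free of the artefact.

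**With the control arm.** Under the same null with both arms fitted, the arm-by-baseline interaction was significant in 4.1% to 5.1% of 5,000 simulated trials per cell (rho 0.7 to 0.9; 20 or 30 per arm). The rebound is the same in both arms and cancels.

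**The case against.** The strongest defence is status and scope. The SAP calls the analysis exploratory and post hoc, and the efficacy claim rests on the group-by-time models, which this does not touch. Most predictor-outcome pairs are free of the artefact, and the text does not explicitly say that each measure will be regressed on its own baseline. All of that stands and limits the point. It does not remove it: an exploratory label warns of chance findings, whereas this is a bias of known direction, and the wording admits own-baseline pairs.

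A second defence is the later multivariable step. Putting own baseline in beside other predictors would deal with coupling carried into those other predictors. The own-baseline coefficient itself would remain coupled, and no arm comparison is named there either.

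A third is Bonferroni. Even if it were extended to 11 tests (alpha 0.05/11, critical value 2.84), rejection at n = 50 would still be about 68%, 49% and 28% at rho 0.6, 0.7 and 0.8. It lowers the rate but does not correct a biased coefficient.

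A reader might also infer more than the SAP supports:

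- **That the worst at baseline will almost certainly be declared responders.** Only the direction is certain. Significance depends on rho and n, and is about 34% at rho 0.9 with n = 50.
- **That later patient selection would be steered by the result.** Nothing in the SAP uses these regressions to select patients.
- **That the change score itself is the fault.** Once own baseline is in a linear model, follow-up and change as outcome give identical coefficients for every other term, including the interaction. The main gap is the missing arm comparison.

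**Conclusion.** The point holds in a limited form. As written, the responder analysis can present a measure's own baseline, or an error-sharing score, as a predictor of gain when there is no benefit, and nothing elsewhere in the SAP prevents this. Using the treated arm alone, or pooling the arms without an interaction, leaves the problem in place.

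The size rests on the assumed rho and n, on equal variances and on a null of no benefit. Under these the false-positive rate runs from 22% (rho 0.9, n = 30) to 91% (rho 0.6, n = 50) instead of 5%. The primary result, demographic predictors and tests with independent errors are outside the point. It merits correction because identifying responders is the paragraph's stated purpose and only wording has to change.

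**What to change.** In the last paragraph of SAP section 1:

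1. Fit both arms in the ITT population, with the outcome measure's own baseline always in the model. Either follow-up score or change may be the outcome. Name the visit.
2. Call a baseline variable, own baseline included, a predictor of treatment response only on its arm-by-predictor interaction. Without that term the model finds predictors of outcome, not of response to treatment.
3. Do not report the own-baseline main effect as a predictor of gain.
4. Report learning-rate and plateau measures from the experimental program as associations within the treated arm only, since they may have no counterpart in the control arm.

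The cost is a change of SAP wording, with the same data and software. The downside is that interaction tests have less power than single regressions, which is acceptable in an exploratory analysis.

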2. CALCULATIONS FROM CRFS

The following calculations must be made from CRF data to create the required data tables. These calculations are performed automatically by scripts that operate on the tables from the EDCS and produce processed data in new tables.

- Posner Cueing Task
 1. Reaction Time Difference for Left - Right trails of *Field Bias* (Left Valid and Invalid RT – Right Valid and Invalid RT)
 2. Reaction Time Difference for Invalid trails or *disengagement* effect ((Left Invalid-Valid RT) – (Right Invalid-Valid RT))
 3. Reaction Times, Averaged Across All Trials (Left Invalid RT, Right Invalid RT, Left Valid RT, Right Valid RT)
 4. Accuracy, Averaged Within and Across All Trials (Left Invalid RT, Right Invalid RT, Left Valid RT, Right Valid RT)
- Pittsburgh Sleep Quality Index
 1. PSQI total (sum of the component scores, DURAT + DISTB + LATEN + DAYDYS + HSE + SLPQUAL + MEDS)
PSQI Component Scores
 2. Sleep Efficiency is calculated in a two-step process
Step 1: Calculate Sleep Efficiency
Sleep Efficiency = [Duration of Sleep/(Difference between GNT and GMT)]*100

Step 2: Recode Sleep Efficiency

- i. IF Sleep Efficiency ≥ 85 , THEN set value to 0
- ii. IF Sleep Efficiency < 85 and ≥ 75 , THEN set value to 1
- iii. IF Sleep Efficiency < 75 and ≥ 65 , THEN set value to 2
- iv. IF Sleep Efficiency < 65 , THEN set value to 3
3. Sleep Disturbance value is calculated based on the sum of (Q5b + Q5c + Q5d + Q5e + Q5f + Q5g + Q5h + Q5i + Q5j)
 - i. If sum = 0, Sleep Disturbance = 0
 - ii. If sum ≥ 1 and ≤ 9 , Sleep Disturbance = 1
 - iii. If sum > 9 and ≤ 18 , Sleep Disturbance = 2
 - iv. If sum > 18 , Sleep Disturbance = 3
4. Duration of Sleep value is recoded based on hours of sleep indicated
 - i. IF Q4 ≥ 7 , Duration of Sleep = 0
 - ii. IF Q4 < 7 and ≥ 6 , Duration of Sleep = 1
 - iii. IF Q4 < 6 and ≥ 5 , Duration of Sleep = 2
 - iv. IF Q4 < 5 , Duration of Sleep = 3
5. Sleep Latency value is calculated in a two-step process

Step 1: Recode Q2 into Q2new

 - i. IF Q2 ≥ 0 and ≤ 15 , Q2new = 0
 - ii. IF Q2 > 15 and ≤ 30 , Q2new = 1
 - iii. IF Q2 > 30 and ≤ 60 , Q2new = 2
 - iv. IF Q2 > 60 , Q2new = 3

Step 2: Calculate and Recode

 - v. IF Q5a + Q2new = 0, Sleep Latency = 0
 - vi. IF Q5a + Q2new ≥ 1 and ≤ 2 , Sleep Latency = 1
 - vii. IF Q5a + Q2new ≥ 3 and ≤ 4 , Sleep Latency = 2
 - viii. IF Q5a + Q2new ≥ 5 and ≤ 6 , Sleep Latency = 3
6. Day Dysfunction Due to Sleepiness is calculated and re-coded as follows
 - i. IF Q8 + Q9 = 0, Day Dysfunction Due to Sleepiness = 0
 - ii. IF Q8 + Q9 ≥ 1 and ≤ 2 , Day Dysfunction Due to Sleepiness = 1
 - iii. IF Q8 + Q9 ≥ 3 and ≤ 4 , Day Dysfunction Due to Sleepiness = 2
 - iv. IF Q8 + Q9 ≥ 5 and ≤ 6 , Day Dysfunction Due to Sleepiness = 3

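### The PSQI Sleep Efficiency formula names as its numerator a variable that the SAP defines only as a 0–3 code, which does not fit the formula's own 85/75/65 cut-offs

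*SAP*

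**What the plan says.** The PSQI scoring rules are in SAP Section 2 (Calculations from CRFs), which states that scripts carry them out automatically on the data tables.

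- **Item 2, Step 1** defines the percentage: "Sleep Efficiency = [Duration of Sleep/(Difference between GNT and GMT)]*100".
- **Item 2, Step 2** turns it into a 0–3 component. The best category is "IF Sleep Efficiency ≥ 85 , THEN set value to 0", and the further cuts are at 75 and 65.
- **Item 4** is the only place where the numerator's name receives values. It opens with "Duration of Sleep value is recoded based on hours of sleep indicated" and then sets "IF Q4 ≥ 7 , Duration of Sleep = 0", "IF Q4 < 7 and ≥ 6 , Duration of Sleep = 1", "IF Q4 < 6 and ≥ 5 , Duration of Sleep = 2" and "IF Q4 < 5 , Duration of Sleep = 3".
- **Item 1** forms the PSQI total from seven abbreviated components, among them DURAT and HSE, without mapping the abbreviations to the items below.

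Section 1 lists both the PSQI total and Sleep Efficiency (raw score) as secondary outcomes. Section 4 puts both, and the component scores, into the Quality of Sleep composite.

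**The concern.** One name does two jobs. In item 2 it has to be a number of hours, because it is divided by a time span and multiplied by 100. In item 4 it is a code that runs the opposite way, falling as sleep lengthens. The quantity the percentage needs, Q4, is missing from the formula.

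Section 2 serves as the programming specification, so names matter. If the names were followed literally, the efficiency component would sit at its worst value for practically everyone. A good sleeper's PSQI total would be too high, and the raw percentage would rise as sleep shortened at a fixed time in bed. The affected quantities are two listed secondary outcomes (the total by inference, since HSE is not mapped) and one composite.

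**Working it through.** The SAP states no numerical result here, so there is no figure to reproduce. The check applies the printed rules under two readings of the numerator.

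**Inputs from SAP Section 2.** Duration code: 0 if Q4 ≥ 7, 1 if 6 to < 7, 2 if 5 to < 6, 3 if < 5. Efficiency code: 0 if ≥ 85, 1 if 75 to < 85, 2 if 65 to < 75, 3 if < 65.

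**Assumptions.** The GNT–GMT difference is taken as hours in bed, because the SAP defines neither abbreviation. The hours slept and the 8 hours in bed are illustrative.

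**Formulas.**
- Code reading: efficiency = 100 × (item 4 code) / hours in bed
- Hours reading: efficiency = 100 × Q4 / hours in bed

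**Results with 8 hours in bed.**

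| Q4 (h) | Item 4 code | Code reading | Step 2 code | Hours reading | Step 2 code | Difference in component |
|---|---|---|---|---|---|---|
| 7.5 | 0 | 0/8 = 0% | 3 | 7.5/8 = 93.8% | 0 | +3 |
| 7 | 0 | 0/8 = 0% | 3 | 7/8 = 87.5% | 0 | +3 |
| 6.5 | 1 | 1/8 = 12.5% | 3 | 6.5/8 = 81.3% | 1 | +2 |
| 5.5 | 2 | 2/8 = 25.0% | 3 | 5.5/8 = 68.8% | 2 | +1 |
| 4.5 | 3 | 3/8 = 37.5% | 3 | 4.5/8 = 56.3% | 3 | 0 |

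The hours reading reaches all four codes. The code reading gives code 3 in every row, and its percentage runs the wrong way.

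**When the code reading can escape code 3.** The percentage must reach 65, so hours in bed must not exceed code / 0.65:
- code 1: 1/0.65 = 1.54 h, impossible for someone who slept at least 6 h
- code 2: 2/0.65 = 3.08 h, impossible for someone who slept at least 5 h
- code 3: 3/0.65 = 4.62 h, possible only for someone who slept under 5 h and was in bed for at most about 4.6 h
- code 0: never, since the percentage is always 0

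Anyone in bed for longer than about 4.6 h is therefore coded 3, however well they slept. On an unweighted grid (3 to 10 h slept, time in bed from the hours slept up to 12 h, quarter-hour steps), 639 of 667 combinations (96%) get code 3 under the code reading, against 307 of 667 (46%) under the hours reading. The grid illustrates the rule and does not forecast trial data.

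**The case against.** The strongest reply is that no competent reader would use the code. Multiplication by 100 and cut-offs at 85, 75 and 65 make sense only for hours over hours. Item 4 speaks of recoding, so a value in hours exists first. The formula also comes before the recode, and *Sleep Efficiency* itself names both the percentage and the variable recoded from it, so reuse of labels is simply this section's habit. Most of this stands: hours slept were almost certainly meant.

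It does not make the printed rule right. Order in the list is no protection, since item 1 sums components that are defined only later. Item 5 shows that the authors could separate raw from recoded values, because Q2 becomes Q2new there. Item 4 makes no such separation.

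Three stronger readings may tempt a reader and are not supported:
- **That the trial's sleep data are already mis-scored.** The scripts are not shown, and nothing in the SAP says that they take the item 4 code rather than Q4.
- **That the sleep results would be reversed.** Even under the code reading, reversal concerns only the raw percentage. A component stuck near 3 would dilute the PSQI total, not turn it round.
- **That the denominator fails when bedtime is before midnight.** The SAP gives neither a clock format nor an order of subtraction, and an ordinary elapsed difference handles this case. GNT and GMT merely lack a definition.

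**Conclusion.** The scoring rule as written is wrong by the SAP's own definitions: its numerator is defined only as a 0–3 code, and with that code the rule's cut-offs are practically unreachable. If the text were followed literally, anyone sleeping at least 7 hours would score 0%, and the efficiency component would be too high by up to 3 points, most for the best sleepers. The same would hold for the PSQI total if HSE is the efficiency component, which the list of components implies but the SAP does not state.

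The size depends on the literal reading and on taking the GNT–GMT difference as hours in bed. The finding itself, that the formula and item 4 do not fit together, depends on neither. The point is confined to secondary sleep outcomes and the Quality of Sleep composite. It has no bearing on the Posner field bias. It should be corrected before the sleep outcomes are analysed.

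**What to change.** In SAP Section 2:

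1. Write Step 1 as: Sleep Efficiency (%) = 100 × Q4 (hours slept) / hours elapsed between GNT and GMT, and say what GNT and GMT stand for.
2. Name the item 4 code DURAT and the Step 2 code HSE, so that neither can be taken for hours or for the percentage.
3. State that the Section 1 outcome Sleep Efficiency (raw score) is the Step 1 percentage, and that only HSE enters the PSQI total.
4. Check that the script uses Q4 and elapsed hours.

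The cost is a few lines of SAP wording and a script check, with at most a small correction to the code. The rules already rely on Q4, GNT and GMT, so no new data are needed.
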